Title: Role of Platelet Rich Plasma in supporting the recovery of post-partum Levator Ani Muscle trauma

Running title: Platelet rich plasma in levator ani muscle trauma

NCT number: **NCT03021954**

Document date: January 15th, 2018

Financial dislaimer: None

STUDY PROTOCOL

Participant Flow

We obtained 245 primigravid women. As many as 85 subjects underwent caesarean section because of clinical indications, 39 subjects were failed to follow the study until the end and 5 subjects were found to have avulsion after 40 days post-partum. Overall, there were 58 subjects who successfully followed the examination until the end of the study.

Study Procedure

- a. All patients who come to Polyclinic in Public Health Center (Puskesmas) will be taken a history and physical examination to determine whether the patient meets the criteria or not,
- b. Patients who met the criteria were provided with information about this study. Patients who are willing will be asked to fill out an informed consent. If the patient refuses to participate in this study, the reasons for refusal must be written,
- c. Randomization was performed and participant were divided into 2 groups (intervention group and control group). Participant will not know the results of randomization. Participant may know the results of randomization at the end of the study,
- d. Initial data collection on study form and approval to participate will be taken. Participants are required to write down their full name, complete address, phone number, and family phone number. This is an attempt to increase the participation rate.
- e. Participant will be examined by ultrasound to assess pelvic floor biometry, perineometry to assess pelvic floor muscle strength,
- f. At delivery day, the participant in intervention group will be taken whole blood for preparation of 32 mL of PRP. After the PRP is ready, it will be injected directly into the levator ani muscle during post-partum perineorrhaphy,
- g. Participant in control group will still have whole blood taken for examination (complete blood count) but no PRP preparation will be carried out. During perrineorrharphy will be injected lidocaine 1%. In this way, it is hoped that the participant will now know that she is in the intervention or control group,
- h. At 40 days and 3 months post- partum, the levator hiatal area was assessed using ultrasound examination and levator ani muscle strength was assessed by perineometry. The ultrasound operator does not know the patient group.

Standard Operational Procedure 1 - Perineometry Examination

- 1. Patient was asked to take off her pant and underwear, then wear what has been provided,
- 2. The perineometer tool used is Peritron TM, this tool has a vaginal sensor with T valve inflation, connecting tube, collar, and display unit,
- 3. Plug in the connecting tube to the display unit,
- 4. Activate Peritron TM by pressing the power button. The screen should shows at zero,
- 5. Select the appropriate mode using 3 WTS (3 way toggle switch). In DISPLAY mode, select NO to select numeric mode. Next in DEVICE mode, select PERI for measurement of pelvic floor muscle strength,
- 6. When using the vaginal sensor, grab the sensor at the tail of the connector on the connecting tube,

- 7. Sensor insertion was performed with the subject in the supine position and place pillow (1-2 pieces) on patient's head, knees formed 90 degrees, 45 degrees between the thighs and the examination bed, knees and feet separated by 30 cm,
- 8. The operator wears gloves. Insert the sensor (wrapped with a condom) until it leaves 1 cm in front of the vagina,
- 9. Then do inflation using a syringe on the T valve, inject air up to 100 cm. Pull back the plunger, turn the valve to position T and release the syringe,
- 10. Press and release the button on the display unit until it shows a zero,
- 11. Ask the subject to 'pinch' the sensor as hard and as long as possible,
- 12. Data will be stored in PEAK, AVERAGE, DURATION, GRADIENT, and AREA UNDER CURVE modes,
- 13. DURATION will be read in seconds, starting from pressure above 5 cmH₂O to below 5 cmH₂O,
- 14. AVERAGE is AREA UNDER CURVE/DURATION.
- 15. PEAK is the maximum value in cmH₂O unit,
- 16. GRADIENT is in cmH₂O. GRADIENT is the maximum value divided by the time it takes to reach the maximum value (to measure onset),
- 17. AREA UNDER CURVE is the length of contraction multiplied by the average value of muscle strength (AVERAGE),
- 18. Remove the sensor,
- 19. Wiping the subject's genital area and allowing the subject to change clothes.

Standard Operational Procedure 2 – Pelvic Floor Ultrasonography Examination

- 1. After perineometry examination, the patient will underwent 3D ultrasonography examination to measure the integrity of the levator ani muscle and levator hiatal area,
- 2. The transducer is wrapped with a condom before placing it on the perineum,
- 3. Imaging is performed when the patient is in a dorsal lithotomy position (the hips are flexed and slightly abducted), after the bladder has been emptied,
- 4. Display a 2D image, position it so that the symphysis pubis, bladder, vagina, anorectal to levator ani are included in the volume which will be displayed in 4D,
- 5. Measure the hiatal area by pressing the point area on the screen and measure the hiatal area by tracing the edge of the hiatal,
- 6. Subjects were asked to do valsalva maneuver 2 times, measuring the left and right LUG (levator urethral gap) distance on 3 central Tomographic Ultrasound Imaging (TUI) images. If the distance is > 25 mm, then there is a levator ani avulsion,
- 7. Wipe the patient's genital area with a tissue and allow the patient to change clothes,
- 8. Ultrasound results will be validated by an expert (which is different from the USG operator).

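### Women with avulsion and women lost to follow-up sit outside the 58 completers, no analysis set keeps them in their arm, and the flow does not reconcile

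*Protocol*

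**What the plan says.** Participant Flow in the protocol starts from 245 primigravid women and gives 85 caesareans. It then says "39 subjects were failed to follow the study until the end" and "5 subjects were found to have avulsion after 40 days post-partum", and ends: "Overall, there were 58 subjects who successfully followed the examination until the end of the study". It gives no number screened out, refusing or randomised, and no count by arm.

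Study Procedure sets the order of events. Eligibility and consent come first (steps a and b). Step c then says "Randomization was performed and participant were divided into 2 groups". On delivery day (step f) the PRP is prepared and "it will be injected directly into the levator ani muscle during post-partum perineorrhaphy". Hiatal area and strength are measured at 40 days and 3 months (step h), where "The ultrasound operator does not know the patient group". The scan in SOP 2 serves "to measure the integrity of the levator ani muscle and levator hiatal area" (step 1). Avulsion is called when the levator-urethral gap exceeds 25 mm (step 6), and a different expert validates the result (step 8).

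The SAP gives a sample size with a 20% drop-out addition and a total of 65, a sampling method, and the tests (Mann-Whitney and Wilcoxon). It names no analysis population, no rule for women with avulsion and no rule for missing outcomes. It refers to inclusion and exclusion criteria but does not reproduce them.

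**The concern.** The five women are listed beside the caesareans and losses and apart from the completers. Avulsion found after 40 days is a finding made after allocation and after the delivery-day injection, and it comes from the same examination that gives hiatal area. If the injection affects avulsion or its healing, removing these women makes the remaining arms non-comparable. If it does not, no bias is expected, but the result no longer covers women with avulsion, in a trial about recovery from trauma to that muscle.

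The 39 women who did not complete raise the same question on a larger scale: nothing in the SAP says how they enter the comparison. In addition, the counts in Participant Flow do not add up, so a reader cannot tell what share of the randomised women the 58 completers represent.

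**Working it through.** **Flow.** Inputs are from Participant Flow, with the categories taken as non-overlapping.
- Expected completers: 245 - 85 - 39 - 5 = 116. Stated: 58. The stated figure is not reproduced.
- Unexplained: 116 - 58 = 58 women; 58/245 = 24%.
- If the five are already counted among the 39 or the 58, the gap is 245 - 85 - 39 - 58 = 63. Overlap widens the gap.
- 116 is exactly 2 x 58, so a per-arm reading of 58 would close the gap (see the objection).

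**Number randomised.** It is not stated.
- If the 39 were randomised: at least 58 + 5 + 39 = 102. Losses are up to 39/102 = 38% and completers at most 58/102 = 57%.
- If randomisation preceded delivery, as the steps are listed, the caesareans count too: at least 102 + 85 = 187 and at most 245. Completers are 58/187 = 31% down to 58/245 = 24%.
- The SAP's allowance is 20%: 27 x 2 = 54, and 54 x 1.2 = 64.8, which gives its total of 65.

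**Effect of leaving out the five.** The following are assumptions with no source in the documents: 29 completers per arm (58/2), and avulsed women worse by e, equal to 1 to 2 SAP target differences (5-10 for area, 9-18 for strength). The SDs are the SAP's, 6.09 and 11.63. With k of the five in one arm:

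shift = e x [k/(29 + k) - (5 - k)/(34 - k)]

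The bracket is 3/32 - 2/31 = 0.0292 for 3:2, 4/33 - 1/30 = 0.0879 for 4:1, and 5/34 = 0.1471 for 5:0. The standard error of the arm difference is 6.09 x sqrt(2/29) = 1.60 for area and 11.63 x sqrt(2/29) = 3.05 for strength.

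| Split | Area shift | In SE | Strength shift | In SE |
|---|---|---|---|---|
| 3:2 | 0.15-0.29 | 0.09-0.18 | 0.26-0.53 | 0.09-0.17 |
| 4:1 | 0.44-0.88 | 0.27-0.55 | 0.79-1.58 | 0.26-0.52 |
| 5:0 | 0.74-1.47 | 0.46-0.92 | 1.32-2.65 | 0.43-0.87 |

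The SAP plans a Mann-Whitney test. On that scale (the probability that a woman in one arm exceeds a woman in the other, with normal outcomes), the shift is the bracket x [Phi(e/(SD x sqrt 2)) - 0.5]. For area this is 0.006-0.011 at 3:2 and 0.032-0.055 at 5:0. Against a null standard error of about 0.073, that is 0.09-0.15 and 0.44-0.75 standard errors, a similar picture.

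If avulsion is unrelated to arm, the split probabilities are 2 x C(5,k)/32: 62.5% for 3:2, 31.3% for 4:1 and 6.3% for 5:0.

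**The case against.** **Exclusion of the five is an inference.** The protocol says they were found to have avulsion, which the scan records anyway, and an unreproduced criterion may exclude avulsion. This stands as a limit: a reader might conclude that the five were certainly dropped improperly, and the documents do not show that. They do show the five set apart from the completers, and no rule that keeps them in.

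**Bias may be absent.** Avulsion may have occurred at delivery, before the injection, and no scan is listed between delivery and day 40. The masked operator and separate validator largely answer differential detection. Both points stand. What remains is a possible true effect of the injection, which cannot be judged without counts by arm.

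**The gap of 58 need not be an error.** Refusals are expected before randomisation ("If the patient refuses to participate in this study, the reasons for refusal must be written"), and some women may have been ineligible. A reader might infer that 58 women vanished after randomisation; the documents do not support that. The flow is unreconciled rather than shown to be false. The per-arm reading (2 x 58 = 116) would close the gap, but the sentence begins with *Overall*, and 116 far exceeds the planned 65.

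**Attrition could look mild.** Since 58 + 5 = 63 is close to 65, one might infer that about 65 women were randomised and nearly all completed. That requires that none of the 39 was randomised, which fits poorly with their being described as failing to follow the study to its end.

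**Conclusion.** The point holds in a limited form. On the natural reading, the analysis covers completers without avulsion, a group formed partly after allocation and injection, and the SAP has no analysis set to prevent this. The five women alone probably shift the result little: under the assumed avulsion effects, 0.09-0.18 standard errors for area at the likeliest split. Values up to 0.92 need all five in one arm, through a real arm difference or an unlucky split. A claim that dropping them materially biases the trial goes beyond the documents, and the direction is unknown.

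The 39 losses are the larger threat, on the condition that they were randomised: up to 38% lost and at most 57% completing, or 24-31% completing if randomisation came before delivery. Separately, and whatever the analysis set, the flow leaves 58 of 245 women without a stated reason and omits the number randomised. This should be fixed. Confidence is medium on the avulsion point and high on the flow arithmetic.

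**What to change.** 1. **Analysis set.** Make the main analysis all randomised women with a vaginal birth and any 40-day or 3-month measurement, in their allocated arm, including those with avulsion. Do not also condition on perineorrhaphy without showing its counts by arm: it follows allocation, and delivery staff are not stated to be masked. Report avulsion by arm and visit, and keep the analysis without avulsed women as a sensitivity analysis. If a written criterion excludes avulsion found post-partum, cite it and still report both analyses.
2. **The 39 losses.** Report arm and last visit attended, use any 40-day value, and repeat the comparison over a stated range of values for the missing outcomes.
3. **Flow.** State the numbers screened, ineligible, refusing and randomised, then caesareans, losses, avulsions and completers by arm. Account for the 58 women at the stage where they left, and say whether 58 completers is the total.

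The cost is analysis and reporting work, with no new procedure. Because the protocol already reports completed follow-up, the analysis set must be labelled post hoc. Some women will lack 3-month values. Variance may rise slightly: with all five in one arm and the top of the assumed range, that arm's SD goes from 6.09 to sqrt(6.09^2 + (5/34)(29/34) x 10^2) = 7.0 for area, and from 11.63 to sqrt(11.63^2 + (5/34)(29/34) x 18^2) = 13.3 for strength.

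### As written, women are randomised before delivery, although either injection can be given only at perineorrhaphy, and the planned 65 allows nothing for caesarean or no repair

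*Protocol*

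**What the plan says.** The Protocol's Study Procedure is a lettered sequence.

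- **Steps a and b** are screening and consent at the clinic: "All patients who come to Polyclinic in Public Health Center (Puskesmas) will be taken a history and physical examination".
- **Step c** is allocation: "Randomization was performed and participant were divided into 2 groups (intervention group and control group". No date or place is given.
- **Step d** is the study form.
- **Step e** is baseline: "Participant will be examined by ultrasound to assess pelvic floor biometry, perineometry to assess pelvic floor muscle strength".
- **Step f** opens delivery day with the arm already known: "At delivery day, the participant in intervention group will be taken whole blood for preparation of 32 mL of PRP". The product is then given at one point only: "it will be injected directly into the levator ani muscle during post-partum perineorrhaphy".
- **Step g** gives the control arm lidocaine 1% at the same repair. Control blood is taken for a blood count only.

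Allocation is withheld from the participant (step c) and from the ultrasound operator (step h). Nothing is said about staff who manage the birth or perform perineometry.

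The Participant Flow begins "We obtained 245 primigravid women" and continues "As many as 85 subjects underwent caesarean section because of clinical indications". It then lists 39 women with incomplete follow-up, 5 with avulsion found after 40 days, and 58 who completed.

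The SAP names an online randomiser without saying when it is used. It adds 20% for dropout to reach 65, defines no analysis set, and does not say how women who were randomised but not treated are handled.

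**The concern.** Between step c and steps f and g a woman may have a caesarean or may need no perineal repair. In either case neither arm's treatment can be given. If randomisation happens where the protocol puts it, these women have been allocated and then either drop out of the comparison or stay in it untreated. The sample size allows for neither.

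Two further steps come after allocation on this order. One is the decision to repair, which determines who can be treated. The other is baseline muscle strength, a maximal voluntary squeeze (Standard Operational Procedure 1, step 11) that depends on effort and coaching. If the staff concerned know the arm, either could be influenced. Placing allocation later removes both exposures.

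**Working it through.** **1. The SAP's own total.** The SAP's formula is n per arm = 2 × ((1.64 + 1.28) × SD / difference)².

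- Strength: 2 × (2.92 × 11.63 / 9)² = 28.5, so 29; the SAP states 27.
- Hiatal area: 2 × (2.92 × 6.09 / 5)² = 25.3, so 26; the SAP states 23.
- Total: 2 × 27 × 1.20 = 64.8, so 65. This reproduces from the stated 27.

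The differences in n per arm are a separate matter. I use the SAP's 27 per arm (54 evaluable) below. The 65 contains a dropout allowance and nothing else.

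**2. Caesarean share.** From the Participant Flow, 85/245 = 34.7%, leaving 245 − 85 = 160 without caesarean. Vaginal births without repair are not counted, so the share who cannot be treated is at least this.

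**3. If the 65 are counted at step c** (assumption: the 34.7% applies to them and every vaginal birth has a repair):

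- reach vaginal birth: 65 × 160/245 = 42.4, about 21 per arm;
- evaluable after the SAP's 20% dropout: 42.4 × 0.80 = 34.0, about 17 per arm.

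**4. Power for strength**, one-sided 5%, normal approximation: power = Φ(difference / (SD × √(2/n)) − 1.645).

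| Evaluable | n per arm | 9 / (11.63 × √(2/n)) | Power |
|---|---|---|---|
| 54 (as planned) | 27 | 2.84 | 88% |
| 34 | 17 | 2.26 | 73% |

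The target is 90%. For hiatal area (difference 5, SD 6.09), 34 evaluable women give about 77%.

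**5. Keeping untreated women in the analysis does not recover the power.** Suppose untreated women have no treatment effect and the SD is unchanged (assumptions). The expected strength difference becomes 9 × 160/245 = 5.88. With 27 per arm the power is Φ(5.88/3.17 − 1.645), about 58%.

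**6. Numbers needed for 54 evaluable women:**

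- randomised before delivery: 54 / (160/245) / 0.80 = 103.4, so 104;
- randomised once repair is decided: 54 / 0.80 = 67.5, so 68. The SAP's 65 comes from multiplying by 1.20 instead of dividing by 0.80.

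**7. The flow does not close.** 245 − 85 − 39 − 5 = 116, not 58. Since 116 = 2 × 58, the 58 may be a per-arm count, or 58 women are unaccounted for. The text does not say which. Steps 1 to 6 do not use this figure.

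**The case against.** **The timing is inferred.** Step c has no date or place, and letter order is not a perfect guide to chronology: step d takes approval to participate after randomisation, although consent is step b. The SAP recruits consecutive eligible women up to its target, and allocating 245 would be nearly four times 65. The flow would also fit 245 women followed to delivery, with caesareans removed before allocation. The eligibility criteria are not in the documents, so this cannot be checked. This limits what can be said about the 245, but it does not rescue the text. Step f presupposes an allocation, and no later eligibility check or randomisation is described.

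**A reader might infer that over a third of randomised women could never be treated.** The documents do not support that as fact, because the 245 are described as obtained, not as randomised.

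**A reader might infer that the comparison is biased.** The documents do not show this. Participants are blind, the caesareans are attributed to clinical indications, and no loss is given by arm. The route to bias rests on silence about staff blinding.

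**A reader might infer that chance imbalance leaves an arm short.** If 58 is the total, the smaller arm falls below 27 with probability about 45% to 51%, but this is not a measure of lost power. The effective size per arm is 2ab/(a + b): a 26/32 split gives 2 × 26 × 32/58 = 28.7, and 22/36 gives 27.3. The chance that it falls below 27 is only about 2% to 5%. If 58 is per arm, the issue disappears.

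**Later randomisation is a partial and not quite free remedy.** This stands. The 5 avulsions were found after delivery and the 39 incomplete cases are undated, so it does not remove these losses. The control draw is for a blood count only, so the PRP draw cannot be treated as already in place for both arms.

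**Conclusion.** The point holds on the protocol as written. Randomisation precedes delivery, treatment depends on an event that many women will not have, and the sample size ignores this. If the 65 are counted at step c, about 34 evaluable women remain, with one-sided power for strength of about 73% against a planned 90%. That figure assumes the recruited group's caesarean share, repair at every vaginal birth and 20% later loss; any births without repair would make it worse. It describes the plan as written and is not a statement about the power achieved, since 245 women were recruited.

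Caesarean loss unrelated to arm costs mainly power and balance. Bias through the repair decision or baseline strength is a possibility that the plan leaves open, with no computable size or direction. If allocation actually took place after birth, the 34.7% is loss before randomisation and the defect is confined to the wording of step c.

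**What to change.** 1. Complete baseline ultrasound and perineometry (step e) before allocation.
2. Move step c to the delivery day, after vaginal birth and once perineorrhaphy is decided.
3. Count the 65 from that point (68 if the 20% is applied by dividing by 0.80).
4. Define the analysis set in the SAP as all women randomised at that point, analysed by allocated arm.
5. State whether the staff who decide on repair and those who perform perineometry know the allocation.
6. Report the time of randomisation, the numbers randomised per arm, and losses by arm and reason, including the 39 and the 5. State whether 58 is a total or per arm. For women already enrolled, this reporting is the only part still open.
7. If randomisation in fact took place after birth, correct step c to say so.

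**Cost.** No extra patients or visits are needed to make the move. Allocation has to be opened in the delivery room, and PRP preparation starts only after it. The site should settle the logistics of the blood draw, because the control draw is at present only for a blood count. Losses after delivery remain and are handled by items 4 and 6, not by the change in timing.

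### Participant masking is not secured by the procedures described, so the effort-dependent strength outcome is open to expectation bias

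*Protocol*

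**What the plan says.** Protocol, Study Procedure, step c states without qualification: "Participant will not know the results of randomization". Steps f and g describe what each arm undergoes.

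- **Intervention (step f).** On delivery day "the participant in intervention group will be taken whole blood for preparation of 32 mL of PRP", and once prepared "it will be injected directly into the levator ani muscle during post-partum perineorrhaphy".
- **Control (step g).** "Participant in control group will still have whole blood taken for examination (complete blood count) but no PRP preparation will be carried out". For the injection: "During perrineorrharphy will be injected lidocaine 1" (a 1% solution).

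Step g then gives the purpose of these arrangements: "it is hoped that the participant will now know that she is in the intervention or control group". The word *now* is presumably a slip for *not*. Read that way, step g expresses a hope where step c makes a statement.

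On assessors, step h says: "The ultrasound operator does not know the patient group". Nothing is said about the perineometry operator. Strength is measured by SOP 1, step 11: "Ask the subject to 'pinch' the sensor as hard and as long as possible". The SAP, under Estimated Sample Size, sizes the trial on hiatal area during Valsalva and on contraction strength; the larger number, for strength, sets the total.

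**The concern.** Step g relies on two devices to mask the participant: every woman has blood taken, and every woman is injected. Neither device is matched as written. The draws serve different purposes and need different amounts of blood. The injectates are different substances. A site is given for PRP and none for lidocaine, and the documents do not say whether women in the PRP arm also receive lidocaine. No screen, opaque syringe, matched volume or check of participants' beliefs is described.

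This matters most for strength. A woman who believes she had the active treatment may squeeze harder, or one who believes she did not may squeeze less hard, and the perineometer records effort as strength. Masking every assessor would not remove that route. A trial reported as participant-blinded on the strength of step c would also claim more than steps f and g support.

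**Working it through.** **1. The arms side by side**

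| | Intervention (step f) | Control (step g) |
|---|---|---|
| Purpose of blood draw | 32 mL of PRP | complete blood count |
| Volume of blood drawn | not stated | not stated |
| Injectate | PRP | lidocaine 1% |
| Site | levator ani | not stated |
| Volume injected | not stated | not stated |
| Lidocaine given | not stated | yes |
| Syringe or draw concealed | not stated | not stated |

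**2. The blood draw**

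If a share y of the blood is recovered as PRP and nothing is added to it (the documents mention no additive), blood needed = 32 / y.

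- y = 1 (the floor): 32 mL
- y = 0.5 (assumed): 32 / 0.5 = 64 mL
- y = 0.1 (assumed): 32 / 0.1 = 320 mL

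If 32 mL is instead the volume of blood drawn, the figure is again 32 mL, so the floor holds on either reading. The documents give no volume for a blood-count sample. For an assumed 3 to 10 mL, the floor is 32 / 10 = 3.2 to 32 / 3 = 10.7 times as large. Only the direction is robust; the ratio depends on the assumed volumes.

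**3. The planned size for strength**

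Inputs from the SAP: difference 9, SD 11.63, Zα = 1.64 (one-sided 5%), Zβ = 1.28.

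n = 2 × [(1.64 + 1.28) × 11.63 / 9]² = 2 × (3.773)² = 28.5, so 29 per group. The SAP states 27, which is 2 fewer. The stated total follows from 27: 2 × 27 × 1.2 = 64.8, rounded to 65. The SAP's 27 is used below.

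**4. What a spurious shift would do**

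The documents give no size for an expectation effect, so the shifts b are assumed. With no true effect, and a normal approximation to a comparison of means:

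- SE = 11.63 × √(2/27) = 3.17
- One-sided rejection rate = 1 − Φ(1.645 − b/SE)

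| Assumed shift b | b as share of planned 9 | One-sided 5% test | Two-sided 5% test |
|---|---|---|---|
| 0 | 0% | 5.0% | 5.0% |
| 1 | 11% | 9.2% | 6.2% |
| 2 | 22% | 15.6% | 9.7% |
| 3 | 33% | 24.3% | 15.8% |

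The SAP plans a Mann-Whitney test, so these rates indicate scale and are not exact for that test.

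**The case against.** The strongest reply is that nothing here shows a woman would identify her arm. Each participant sees only her own procedures. Both arms have a draw and an injection, and the injection is given during a repair that both arms undergo. The control volumes are unstated, so a matched draw or a concealed syringe is undescribed, not excluded. Step g claims only a hope. All of this stands, and it rules out several stronger readings that a reader might infer.

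- **That masking is impossible.** The documents do not say what women knew about expected volumes or what they could see.
- **That a wait for PRP reveals the arm.** Step f places the draw on delivery day and the injection after preparation, but does not say whether the draw precedes birth. A noticeable wait is not established.
- **That the draws differ by some large known factor.** Any ratio rests on yields and tube sizes from outside the documents.
- **That hiatal area is equally affected, or that it is a clean benchmark for the strength result.** The ultrasound operator is stated to be masked, and SOP 2, step 8 has the results validated by a different expert, so the concern is weaker there. But Valsalva also depends on the participant, so hiatal area cannot serve as an unaffected comparator.

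The perineometry operator might also be the masked ultrasound operator; the documents do not say. Even so, a masked operator would not remove the participant's own expectation.

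What survives the reply is that step c states a mask, and the procedures given to support it do not secure it.

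**Conclusion.** The concern holds in this form: as written, steps f and g do not secure the participant masking stated in step c. Strength, which sets the planned sample size, depends on effort and has no stated masking of either the participant's procedures or the perineometry operator.

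The unequal demands on the blood draw follow from the documents in direction, with a floor of 32 mL for undiluted PRP. The size of any bias is unknown. The rise to about 9%, 16% or 24% shows only that shifts of one ninth to one third of the planned difference would matter at this sample size; it is not an estimate of what happened. This deserves a change to the procedures and to the blinding claim, but it does not invalidate the trial.

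**What to change.** 1. **Steps f and g.** Screen the blood draw and the injection from the participant's view and use opaque-sleeved syringes in both arms, without altering the clinical procedure or its timing.
2. **Check the mask.** Record each woman's guess of her arm, with a *don't know* option, soon after the repair, before perceived recovery can shape the answer. If the question is repeated at 40 days or 3 months, ask it after perineometry so that it does not prompt effort. Report guesses by arm.
3. **Limit the claim.** Unless there is evidence that masking worked, describe only the ultrasound operator as masked, and report any strength benefit with the caveat that expectation may contribute. Participant Flow already reports 58 women as having completed; for women already followed up, only this reporting change and the clarifications in item 4 are still possible.
4. **Reconcile and state.** Say whether 32 mL is blood drawn or PRP obtained. State what was drawn and injected in each arm, including volumes, sites and lidocaine use, and whether the perineometry operator was masked. What those clinical details should be is for the investigators.

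The cost is protocol wording, syringe sleeves and screens, and one extra question. The downside is a weaker blinding claim if women guess correctly or if no evidence on masking exists.
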